# 4.5 Safety Analyses

Safety analyses include exposure, AEs, clinical laboratory results, vital signs, and ECGs. Safety events and findings will be summarized by treatment group. Erroneously treated participants (eg, those randomized to treatment A but actually given treatment B) are accounted for in the treatment group with the majority estimated usage. The majority estimated usage will be determined based on which treatment had more kits dispensed (not including kits returned unused). In the case of a tie, the randomized treatment will be used for safety analyses. In all cases, the dose group will be the same as randomized dose level.

Tables are provided for the safety set and listings are provided for all participants or the safety set depending on the availability of data.

Laboratory, vital sign, and ECG interval abnormalities will be considered treatment emergent if collected after the first dose and if the result is numerically more extreme than baseline – ie, the result is lower than baseline for low abnormalities and higher than baseline for high abnormalities. In cases of a missing baseline value (and for all random glucose abnormalities, since there is no planned baseline), any post-baseline value meeting the post-baseline criteria will be considered to be an abnormality. Treatment-emergent increase in urinalysis defined as change from negative/trace at baseline to ++, +++, or ++++ at any visit after baseline or an increase of at least ++.

## **4.5.1 Exposure**

## **4.5.1.1 Definitions and Derivations**

As per the CSP, participants start the subcutaneous injections of the study IP at day 1. Study IP is dispensed to the participant for self-administration at home.

Exposure (days) is calculated only for participants in the safety population as the total number of days on study drug (ie, gaps in dosing due to study drug interruption will not be taken-out from the calculation). Exposure is calculated as the study drug dose last date minus study drug dose first date plus 1.

Cumulative exposure (days) is also computed based on exposure, using the following duration (days) categories:

- 12 weeks (≥ 84 days)
- 24 weeks (≥ 168 days)
- 48 weeks (≥ 336 days)

#### 4.5.1.2 Presentation

Exposure duration and cumulative exposure will be presented in a summary table for each treatment group. Maximum titrated dose (n % at each dose) will be summarized for each treatment group. The tables will be based on the safety population.

Exposure will be listed for the safety population.

## 4.5.2 Adverse Events

#### 4.5.2.1 Definitions and Derivations

AEs will be coded with MedDRA version 25.0 or later. Additional details on AE reporting are provided in the CSP.

AEs of special interest (AESIs) for this study include:

- Nausea
- Vomiting
- Increased Heart Rate
- Injection Site Reaction
- Blood Pressure Alteration (Hypotension/Hypertension)
- Hypoglycemia
- Diabetic ketoacidosis
- Anti-drug Antibody

- Pancreatitis
- Pancreatic carcinoma
- Thyroid Carcinoma
- Acute Renal Failure Secondary to Dehydration
- Drug-induced liver injury (DILI)
- Cardiovascular events
- Gallbladder-related disease

The duration of an AE is calculated as the end date of the AE - start date of the AE + 1. Duration is calculated for complete dates only. Imputed dates should not be used. If one of the dates is missing or partially missing, the duration is missing.

3-point and 5-point MACEs are defined as a composite of the below adjudicated events.

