## 8.3.6 Adverse Events of Special Interest

An AESI is one of scientific and medical interest specific to understanding of the IP and may require close monitoring and collection of additional information by the investigator. An AESI may be serious or non-serious. The rapid reporting of AESIs allows ongoing surveillance of these events in order to characterize and understand them in association with the use of this IP.

Adverse events of special interest for this study include:

- Nausea
- Vomiting
- Increased heart rate
- Injection site reaction
- Blood pressure alteration (hypotension/hypertension)
- Hypoglycemia
- Diabetic ketoacidosis
- Anti-drug antibody
- Pancreatitis
- Pancreatic carcinoma
- Thyroid carcinoma
- Acute renal failure secondary to dehydration
- Drug-induced liver injury
- Cardiovascular events
- Gallbladder-related disease

These AESIs are to be reported as described in Section 8.3.1 and Section 8.3.2. Information on AESIs of hypoglycemia, diabetic ketoacidosis, injection site reaction, pancreatitis, pancreatic carcinoma, thyroid carcinoma, drug-induced liver injury, and CV events should be reported in the appropriate eCRF. Participants with significant vomiting should be monitored for electrolytes. Refer to Section 6.5.3 for a discussion of gastrointestinal tolerability and mitigating strategies. Hepatic enzyme abnormality meeting the definition of PHL is also considered an AESI. Refer to Section 8.3.8 for the definition and reporting of AESIs of hepatic enzyme abnormality.

Refer to the IB for a discussion of potential risks.

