# E 4.2 Potential Hy's Law Criteria met

If the participant does meet PHL criteria the investigator will:

- Notify the AstraZeneca representative who will then inform the central Study Team
- Within 1 day of PHL criteria being met, the investigator will report the case as an SAE of PHL; serious criteria 'Important medical event' and causality assessment 'yes/related' according to CSP process for SAE reporting.
- For participants that met PHL criteria prior to starting IMP, the investigator is not required to submit a PHL SAE unless there is a significant change# in the participant's condition.
- The Study Physician contacts the investigator, to provide guidance, discuss and agree an approach for the study participants' follow-up (including any further laboratory testing) and the continuous review of data.
- Subsequent to this contact the investigator will:
  - Monitor the participant until liver biochemistry parameters and appropriate clinical symptoms and signs return to normal or baseline levels, or as long as medically indicated. Completes follow-up SAE Form as required.
  - Investigate the etiology of the event and perform diagnostic investigations as discussed with the Study Physician. This includes deciding which of the tests available in the HL lab kit should be used.
  - Complete the 3 Liver eCRF Modules as information becomes available.

\*A 'significant' change in the participant's condition refers to a clinically relevant change in any of the individual liver biochemistry parameters (ALT, AST, or TBL) in isolation or in combination, or a clinically relevant change in associated symptoms. The determination of whether there has been a significant change will be at the discretion of the investigator, this may be in consultation with the Study Physician if there is any uncertainty.

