#### 4.5.2.2 Presentation

AEs will be summarized for each treatment group. The AE tables will be based on the safety analysis set. Summary tables will include all on-study AEs. Select AE and AESI summaries will be repeated for all on-treatment events as appropriate.

Summary tables are listed below.

An overview table will contain summaries of the number and percentage of participants with the following:

- Any AE
- Any AE considered related to IP
- Any AE leading to death
- Any SAE
- Any AE leading to discontinuation of IP

- Any AE leading to a reduction of IP dose
- Any AE leading to withdrawal from the study

The following summary tables will be presented by SOC and PT:

- Any AE
- Any AE considered related to IP
- Any AE leading to death
- Any SAE
- Any AE leading to discontinuation of IP
- Any AE leading to a reduction of IP dose
- Any AE leading to withdrawal from the study
- The number and percentage of participants with any AEs by maximum reported intensity

On-study AESIs will be summarized as number and percentage of participants with the following:

- Any AESI
- Each specific AESI will also be summarized, overall and by maximum intensity
- Each specific AESI will be summarized by SOC and PT
- Select AESI summaries will be repeated for all on-treatment events as appropriate

Adjudicated events (separate on-study and on-treatment analyses) will be summarized as number and percentage of participants with the following:

- Any liver event (hepatic decompensation, clinical cirrhosis, DILI, hepatocellular carcinoma, or death from any cause)
- Events of hepatic decompensation
  - Clinically apparent ascites requiring treatment
  - Complication of ascites (eg, spontaneous bacterial peritonitis, diuretic-resistant ascites [refractory ascites], hepato-pleural effusion)
  - Hepatic encephalopathy of Grade 2 or above (according to the West Haven criteria) requiring treatment
  - Portal hypertension-related upper gastrointestinal bleeding identified by endoscopy and requiring hospitalization, including events of bleeding from esophageal varices, gastric varices, and portal hypertensive gastropathy
- Clinical cirrhosis
- DILI
- Hepatocellular carcinoma

- Death by any cause
- 3-point MACE
- 5-point MACE
- CV death
- Cardiac ischemic events Myocardial Infarction (non-fatal)
- Cardiac ischemic events Myocardial Infarction (any)
- Cerebrovascular events- Stroke (non-fatal)
- Cerebrovascular events- Stroke (any)

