# Potential Hy's Law

AST or ALT  $\geq$  3 × Upper Limit of Normal (ULN) together with TBL  $\geq$  2× ULN at any point during the study following the start of study intervention irrespective of an increase in ALP. Potential Hy's Law cases are determined without regard to the baseline value. The elevation in transaminases must precede or be coincident with (ie, on the same day) the elevation in TBL, but there is no specified timeframe within which the elevation in transaminases and TBL must occur.

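### The SAP's AESI list omits potential Hy's Law hepatic enzyme abnormality, which the protocol names as an AESI, and the departure is not declared

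*SAP*

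**What the plan says.** Protocol 8.3.6 introduces its bullets with "Adverse events of special interest for this study include" and lists 15 items, one of which is drug-induced liver injury (DILI). The paragraph after the bullets adds: "Hepatic enzyme abnormality meeting the definition of PHL is also considered an AESI".

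SAP 4.5.2.1 introduces its own list with "AEs of special interest (AESIs) for this study include" and gives 15 items. SAP 4.5.2.2 builds the tables from that list: "On-study AESIs will be summarized as number and percentage of participants with the following". The rows are an Any AESI line and the individual AESIs, and "Each specific AESI will also be summarized, overall and by maximum intensity".

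In the SAP, PHL appears only under laboratory results. Section 4.5.3.1 defines it as AST or ALT at least 3 × ULN together with total bilirubin at least 2 × ULN after the start of study intervention, and adds: "Potential Hy's Law cases are determined without regard to the baseline value". Section 4.5.3.2 summarizes such cases by treatment and lists them, for both the on-treatment and on-study periods.

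For sites, Protocol Appendix E 4.2 says: "Within 1 day of PHL criteria being met, the investigator will report the case as an SAE of PHL". SAP Section 2 names one departure from the protocol, the per protocol set, and says there are no others.

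**The concern.** The SAP appears to have taken over the protocol's bullets without the sentence that follows them. AESIs are listed among the assessments that make up the primary safety endpoint (Protocol 3.1, SAP 4.2.1), so the tables that report that component would be built on 15 of the protocol's 16 categories.

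The missing category is not the same as the DILI item. PHL is a biochemical threshold that is met before cause is settled, and Appendix E 5 expects that some cases will have an agreed alternative explanation. Such a case belongs among the protocol's AESIs, but the SAP gives it no AESI row and no place in the Any AESI count.

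**Working it through.** No power, sample size or alpha figure bears on this point. The check is a comparison of the texts, followed by one small calculation of size.

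**1. The lists.** Protocol 8.3.6: 15 bullets + 1 item in the following text = 16 categories. SAP 4.5.2.1: 15 categories. All 15 bullets match item for item, so the difference is 16 − 15 = 1, and the unmatched item is PHL.

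**2. Declared or not.** SAP Section 2 mentions only the per protocol set. The SAP amendment history records gallbladder-related disease being added to the AESI list but nothing on PHL.

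**3. Whether the DILI row covers it.** The protocol names DILI and PHL separately in the same section. The SAP gives no rule (preferred terms, laboratory criterion, eCRF page or adjudication result) for what enters the DILI AESI row. Adjudicated DILI goes to the adjudicated-events table in SAP 4.5.2.2, and nothing says that adjudication feeds the AESI rows.

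Cases outside DILI are plausible. Exclusion criterion 25(a) removes AST or ALT of 5 × ULN or more, so a participant may enter between 3 and 5 × ULN. Because PHL ignores baseline, someone who stays at that level could meet the criteria through a later bilirubin rise with an unrelated cause.

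**4. Whether the SAE record is enough to identify cases.** Under Appendix E 5, if the agreed alternative explanation is itself an AE or SAE, the site updates the report and reassesses its term, causality and seriousness. If no alternative is found, the term becomes Hy's Law. A search for the PHL term at database lock can therefore miss cases. Appendix E 6 and E 7 also require no action for some on-treatment occurrences where the participant's condition has not changed significantly, although the SAP's laboratory definition counts them.

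**5. Whether laboratory data alone are enough.** Appendix E 1 lets central and local results count toward PHL. SAP 4.5.3.1 describes the safety tests as performed centrally and does not say whether local results enter the PHL summary. A case found only from laboratory values also has no AE intensity and no preferred term, so it cannot fill an intensity or SOC/PT table.

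Steps 4 and 5 together mean that either source should be sufficient for the flag.

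**6. Size.** With about 55 randomized 2:1:2:1, each cotadutide dose has 55 × 2/6 ≈ 18 participants, and the two placebo groups pooled also have about 18. One case is 1/18 = 5.6 percentage points in its row. If the placebo groups were shown separately, each would have 55 × 1/6 ≈ 9, and one case would be 1/9 = 11.1 points. The documents give no expected PHL count; 0 to 1 is an assumption for a trial of this size. Any AESI changes only if the participant has no other AESI.

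**The case against.** The strongest reply is that nothing is lost. PHL has its own summary by treatment and its own listing for both periods. There are also ALT and AST categories crossed with bilirubin, eDISH plots, and the SAE tables in which a PHL case is first reported. Laboratory assessments are part of the primary safety endpoint too, so the signal reaches that endpoint by another route. This stands, and it limits the consequence to the AESI tables.

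Second, the SAP list is introduced as non-exhaustive and refers to the protocol for further details of AE reporting, so a programmer could add PHL. That is possible, but nothing in the SAP instructs it, and an exact copy of the 15 bullets invites the opposite reading.

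Third, a case with no other explanation is DILI caused by the product and so might fall under the DILI item. This covers only the cases attributed to the product, and the SAP does not state the mapping.

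Fourth, Any AESI includes nausea and vomiting, which Protocol 2.2.2 describes as more frequent on cotadutide than on placebo, so the total is unlikely to move. This also stands.

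A reader might infer that the AESI tables would contradict the PHL laboratory table. They would be discordant, because one counts recorded events and the other counts threshold crossings; different counts from different definitions are not a contradiction. A reader might also infer that PHL is the most serious hepatic signal in the protocol. The documents do not support that: confirmed Hy's Law (Appendix E 2), and hepatic decompensation, liver transplantation and hepatocellular carcinoma (Protocol 8.3.10), are defined separately.

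**Conclusion.** The omission is real and undeclared. Following the SAP as written would undercount a named component of the primary safety endpoint if a PHL case occurred that was not recorded under the DILI AESI. Such a case would still be visible in the laboratory PHL summary and listing.

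The practical effect is small: on the assumption above, 0 to 1 participants, in analyses that SAP 3.3 describes as descriptive with no formal testing. No safety conclusion is shown to depend on it. It is worth correcting because the protocol is explicit, the table belongs to the primary objective, and the change is cheap.

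**What to change.** In SAP 4.5.2.1, add hepatic enzyme abnormality meeting PHL criteria as the sixteenth AESI. Flag a participant who **either** meets the existing PHL definition in 4.5.3.1 **or** has an AE or SAE record of PHL or Hy's Law. In the 4.5.2.2 tables, give it its own row and include it in Any AESI.

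Give maximum intensity, and SOC and preferred term, only where an AE record exists. Footnote cases identified from laboratory data alone, including those that need no PHL SAE under Appendix E 6 or E 7.

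If the sponsor instead intends PHL to be reported only through the laboratory summary, Section 2 should declare that as a departure from Protocol 8.3.6.

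The cost is a short SAP edit, one derived flag, a footnote, and a row that partly duplicates the PHL laboratory table. No new data collection is needed.

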## 3- and 5-point MACE:

- Death by any cause
- Cerebrovascular events- Stroke (non-fatal)
- Cardiac ischemic events Myocardial Infarction (non-fatal)

#### 5-point MACE only:

- Cardiac ischemic events Hospitalization for Unstable Angina
- Hospitalization for heart failure

#### 4.5.2.2 Presentation

AEs will be summarized for each treatment group. The AE tables will be based on the safety analysis set. Summary tables will include all on-study AEs. Select AE and AESI summaries will be repeated for all on-treatment events as appropriate.

Summary tables are listed below.

An overview table will contain summaries of the number and percentage of participants with the following:

- Any AE
- Any AE considered related to IP
- Any AE leading to death
- Any SAE
- Any AE leading to discontinuation of IP

- Any AE leading to a reduction of IP dose
- Any AE leading to withdrawal from the study

The following summary tables will be presented by SOC and PT:

- Any AE
- Any AE considered related to IP
- Any AE leading to death
- Any SAE
- Any AE leading to discontinuation of IP
- Any AE leading to a reduction of IP dose
- Any AE leading to withdrawal from the study
- The number and percentage of participants with any AEs by maximum reported intensity

On-study AESIs will be summarized as number and percentage of participants with the following:

- Any AESI
- Each specific AESI will also be summarized, overall and by maximum intensity
- Each specific AESI will be summarized by SOC and PT
- Select AESI summaries will be repeated for all on-treatment events as appropriate

Adjudicated events (separate on-study and on-treatment analyses) will be summarized as number and percentage of participants with the following:

- Any liver event (hepatic decompensation, clinical cirrhosis, DILI, hepatocellular carcinoma, or death from any cause)
- Events of hepatic decompensation
  - Clinically apparent ascites requiring treatment
  - Complication of ascites (eg, spontaneous bacterial peritonitis, diuretic-resistant ascites [refractory ascites], hepato-pleural effusion)
  - Hepatic encephalopathy of Grade 2 or above (according to the West Haven criteria) requiring treatment
  - Portal hypertension-related upper gastrointestinal bleeding identified by endoscopy and requiring hospitalization, including events of bleeding from esophageal varices, gastric varices, and portal hypertensive gastropathy
- Clinical cirrhosis
- DILI
- Hepatocellular carcinoma

- Death by any cause
- 3-point MACE
- 5-point MACE
- CV death
- Cardiac ischemic events Myocardial Infarction (non-fatal)
- Cardiac ischemic events Myocardial Infarction (any)
- Cerebrovascular events- Stroke (non-fatal)
- Cerebrovascular events- Stroke (any)
- Cardiac ischemic events- Hospitalization for Unstable Angina
- Hospitalization for heart failure
- Diabetic ketoacidosis
- Thyroid carcinoma
- Pancreatitis
- Pancreatic carcinoma

Additional analyses will be provided for adjudicated events, if required.

Where number of participants with AEs are summarized by SOC and PT, participants with multiple events in the same SOC/PT are counted only once in that SOC/PT. Participants with events in more than 1 SOC/PT are counted once in each of those SOCs/PTs. Participants with multiple occurrences of the same AESI will be counted once at the maximum observed severity. Tables will be sorted by international order for SOC and in alphabetical order for PT.

Additionally, the following tables will be presented:

• The number and percentage of participants with non-serious AEs occurring with a frequency > 5.0% in any treatment group for each SOC and PT. This table will be produced as a separate pdf output to meet clinical trial transparency requirements and not for inclusion in the CSR.

A list of key participant information for participants with AEs with outcome of death, participants with SAEs, and participants with AEs leading to discontinuation of IP will be provided. The durations reported in these tables will be derived only for fully completed dates as below:

• Time from first dose of IP to AE (in days) will be calculated as the AE start date minus date of dose +1.

- Time from first dose to death (in days) will be calculated as the date of death minus date of dose +1.
- The same approach will be used for deriving time from start of treatment to AE becoming serious or discontinuation.
- Time from last dose prior to AE start and last dose prior to death will be calculated as the date of death minus the date of last dose prior to AE/death +1.

All AEs will be listed (including AEs before the date of first dose).

# 4.5.3 Clinical Laboratory Results

## 4.5.3.1 Definitions and Derivations

Clinical laboratory safety tests are performed in a central clinical laboratory.

Clinical laboratory safety tests are specified in Table 10, with clinical results to be reported in SI units as well as conventional units where indicated.

Table 10 Laboratory Safety Variables

Hematology/hemostasis (whole blood)	Clinical chemistry (plasma or serum)
B-Hemoglobin (SI: g/L and conventional: g/dL)	S/P-Creatinine (SI: umol/L and conventional: mg/dL)
B-Leukocyte count (10  /L)	S/P-Total Bilirubin (TBL) (SI: umol/L and conventional: mg/dL)
B-Leukocyte differential count (absolute count) (109/L)	S/P-Alkaline phosphatase (SI: μkat/L and conventional: U/L)
B-Platelet count (10  /L)	S/P-AST (SI: μkat/L and conventional: U/L)
B-Red blood cell count (10  /L)	S/P-ALT (SI: μkat/L and conventional: U/L)
B-Hematocrit (ratio)	S/P-Albumin (SI: g/L and conventional: g/dL)
B-Mean corpuscular hemoglobin concentration (SI: g/L and conventional: g/dL)	S/P-Potassium (SI: mmol/L and conventional: mEq/L)
B-Mean corpuscular volume (μm³)	S/P-Calcium, total (SI: mmol/L and conventional mg/dL)
B-Red cell distribution width (fL)	S/P-Sodium (SI: mmol/L and conventional: mEq/L)
B-Red blood cell morphology	S/P-Blood urea nitrogen (SI: mmol/L and conventional: mg/dL)
	S/P-Phosphorous (SI: mmol/L and conventional: mg/dL)
Urinalysis (dipstick)	S/P-Bicarbonate (SI: mmol/L and conventional: mEq/L)
U-Hemoglobin/erythrocytes/blood	S/P-Glucose (mmol/L and mg/dL)

Table 10 Laboratory Safety Variables

Hematology/hemostasis (whole blood)	Clinical chemistry (plasma or serum)
U-Protein	S/P-Chloride (SI: mmol/L and conventional: mEq/L)
U-Microscopic analysis (if positive for blood, nitrites, or protein)	S/P-GGT (SI: μkat/L and conventional: U/L)
U-Glucose	
U-Ketones	
U-pH	
U-Specific gravity (ratio)	
U-Bilirubin	
U-Color	
U-Appearance	
U-Nitrites	
U-Leukocytes	
U-Urobilinogen	
U-Drugs of abuse, standard panel (Screening only)	

ALT, alanine aminotransferase; AST, aspartate aminotransferase; B, blood; GGT, gamma glutamyl transferase; P, plasma; S, serum; SI, International System of Units; TBL, total bilirubin; U, urine.

